3.1 General Design

Study Overview

The study proposed is a prospective trial of controlled SRL monotherapy minimization and withdrawal in up to 25 stable non-immune non-viremic LT recipients. Given the sample size calculations (see Statistical section), we plan to enroll up to 25 SRL monotherapy patients for this study (Figure 1). All patients will be consented to undergo laboratory evaluation as well as an enrollment liver biopsy and blood tests. If the patient meets inclusion/exclusion (I/E) criteria (see below), SRL will be minimized over 6 months until once a week dosing is achieved. Repeat clinical and immunological blood tests as above will be performed, and if no biochemical signs of rejection, SRL will be discontinued with blood tests and liver biopsy 12 months later for similar biochemical, histological and immunological measures. At any concern for rejection, liver biopsy and assays for equivalent biochemical, histological and immunological measures will be performed and if rejection is diagnosed on biopsy, a second attempt at withdrawal **will not** be performed. Patients will be monitored as standard of care with clinic visits every 6 months and laboratory tests every 2 weeks. The total study length will be 18 months: 6 month minimization phase and 1 year follow-up after withdrawal success/failure. The primary outcome will be the proportion of tolerant patients off SRL therapy with normal liver biochemistry and graft histology at 18 months. Secondary outcomes will include the incidence, severity and reversibility of rejection, patient/graft survival, resolution of SRL and other non-specific IS effects, and the assessment of clinical/immunological biomarkers of tolerance. All continuous/categorical clinical variables will be compared with the appropriate statistical analyses. The goal is that the primary and secondary aims will provide valuable preliminary data to further elucidate the mechanisms of mTOR-I immunoregulation and for determining the initial clinical success/feasibility of the mTOR-I approach (vs. historical 20% CNI withdrawal success seen in studies from the Immune Tolerance Network [ITN] and other groups). This is all so as to guide a submission to the Immune Tolerance Network for larger, more adequately powered prospective trials comparing SRL vs. CNI withdrawal and accompanying biomarker predictors of tolerance. If this pilot study fails to show a correlation between our biomarkers and the success/failure of SRL withdrawal, or is associated with an unacceptable low (e.g. <20%) rate of operational tolerance, then this would avoid the necessity for such large, expensive trials and support the continued development of alternative approaches to tolerance.

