After long term (> 3 years post-LT, > 3 months on SRL monotherapy) on SRL monotherapy, inclusion/exclusion criteria will be reviewed and if appropriate, consent as above will be obtained. If the patient agrees and signs consent, baseline standard of care screening laboratories complete blood count, comprehensive metabolic panel, sirolimus (CBC, CMP, SRL trough level, fasting lipid profile, hemoglobin A1C [HbA1C], urine protein/creatinine ratio) and non-standard of care biomarker assays (blood immunophenotyping, proteogenomics) and liver biopsy (histology and graft immunohistochemistry) will be performed as dictated by the protocol. In addition, the liver biopsy will be used to determine stability in graft function (i.e. no evidence of rejection or immune-mediated hepatitis) before considering minimization/withdrawal. SRL minimization/withdrawal will only be performed if clinically, biochemically and histologically [by biopsy; liver transplant pathology read ([name], [name])] stable. Throughout the entire study, liver function tests will be monitored every 2 weeks (monthly is standard of care, so the interim non-standard of care 2 week blood tests will be covered by the study funds). Patients entering the minimization/withdrawal phases will be reduced by a total dose of 50% of their baseline dose every month until patients are on 0.5 mg SRL daily. At this point, every other day dosing will begin x 1 month. If no LFT abnormalities, twice weekly dosing x 1 month, then once a week dosing x 1 month. Prior to complete discontinuation, repeat clinical (screening labs above) and blood biomarker assays (blood immunophenotyping, proteogenomics) will be performed. Liver biopsy will not be performed at this juncture unless there are biochemical signs of liver injury. If complete withdrawal is deemed safe (no evidence of biochemical abnormalities) patients will be withdrawn completely (i.e. the once/week SRL dose discontinued) and followed off IS therapy for one year. In this time period, liver function tests will be monitored every 2 weeks, as usual, and repeat clinical (screening labs above), liver biopsy and blood (blood immunophenotyping, proteogenomics) assays performed at the end of this year or at any concern for rejection.

Blood and Tissue Samples

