Standard of care laboratories (CBC, CMP) will be performed every month on all patients, and only LFTs performed in the interim 2 weeks between each month (non-standard of care; covered by the study funds) until complete withdrawal. 3 green top 5 mL and 3 red top 5 mL tubes of blood for biomarker assays will be taken on all patients prior to study enrollment, prior to complete withdrawal, and one year after withdrawal or at the time of suspected rejection. Liver biopsy (one 3 cm biopsy- 2 cm for histology and 1 cm for genomic assays) will be performed at baseline (pre-minimization) and 1 year post withdrawal. A separate clinical informed consent will be obtained each time a liver biopsy is performed. If the patient develops elevation in liver transaminases requiring a liver biopsy at any stage of the study protocol, blood (all for immune monitoring (IM) assays) will be requested from the patient at the time of the biopsy. If rejection occurs, the patient will be followed in the study until completion but not be further withdrawn from SRL or have a liver biopsy at the end of the study

Follow-up

Laboratory follow-up is described above- every 2 weeks throughout the trial until complete withdrawal. Any biochemical (or clinical) signs or significant liver function test abnormalities will be acted on immediately either by liver biopsy or a pause in IS withdrawal per investigator discretion. All patients will be seen in the clinic every 3 months to assess for any new signs or symptoms or resolution of drug side effects in the minimization or withdrawal arm. Quality of life questionnaires; Post Liver Transplant

Quality of Life Instrument (pLTQ) and the Promis-29 profile v1.0 will be administered at the study onset and after successful vs. unsuccessful withdrawal (end of study)

Outcome Measures

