any patient throughout the study developing liver dysfunction (direct bilirubin >1 mg/dL; ALT, AST, or AlkPhos > 2xULN), this will be confirmed on a repeat blood test within 1-2 weeks and if persistent, liver biopsy will be performed. Immediately before complete withdrawal, i.e. repeat clinical (screening labs) and blood assays will be performed. If complete withdrawal is deemed safe (no evidence of biochemical abnormalities, i.e. direct bilirubin < 1 mg/dL; ALT, AST, or AlkPhos < 2xULN), patients will be withdrawn completely (i.e. the once/week SRL dose discontinued) and followed off SRL therapy for one year. In this time period, liver function tests will be monitored every 2 weeks. At 12 months following withdrawal, the same history and physical, QOL survey, screening labs and blood IM assays will be performed as in the study initiation, as well as the liver biopsy- all for the primary endpoint. If rejection or immune-mediated hepatitis is seen on this post-withdrawal biopsy or at any time during the study period, the patient will be reinitiated on IS therapy appropriately per the PI and not have another withdrawal attempt. All patients will be followed until 1 year post-attempted withdrawal, even if unsuccessful, although patients developing rejection or resumption of IS prior to this period will not have a final liver biopsy performed (i.e. only those presumed tolerant or who did not have rejection).

Blood and Tissue Samples

Standard of care laboratories complete blood count, liver function tests (CBC, LFTs) will be performed every 2 weeks on all patients. Please see Figure 1 above for sample collections. A separate clinical informed consent will be obtained each time a liver biopsy is performed. If the patient develops elevation in liver transaminases requiring a liver biopsy at any stage of the minimization/withdrawal phase, blood assays will be requested from the patient at the time of the biopsy. These immunological data in rejecting patients will be important to compare to patients who successfully are minimized and withdrawn.

Follow-up

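### Two sentences in Section 3.1 stop two-weekly liver tests when sirolimus stops; the rest of the protocol continues them through the year off drug

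*Combined protocol and SAP*

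**What the plan says.** Two sentences in Section 3.1 end the two-weekly schedule at complete withdrawal:

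- Blood and Tissue Samples sets monthly standard-of-care panels for all patients, with "only LFTs performed in the interim 2 weeks between each month (non-standard of care; covered by the study funds) until complete withdrawal".
- Follow-up sets laboratory follow-up "every 2 weeks throughout the trial until complete withdrawal".

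The screening text of the same section fixes what complete withdrawal means: "patients will be withdrawn completely (i.e. the once/week SRL dose discontinued) and followed off IS therapy for one year". It continues: "In this time period, liver function tests will be monitored every 2 weeks, as usual". It also explains who pays: "monthly is standard of care, so the interim non-standard of care 2 week blood tests will be covered by the study funds".

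The other statements of the schedule contain no cut-off:

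- The Study Overview in 3.1 gives "laboratory tests every 2 weeks".
- Section 4.3 has patients "followed off SRL therapy for one year. In this time period, liver function tests will be monitored every 2 weeks". Its Follow-up text is close to the 3.1 Follow-up sentence but lacks the limiting phrase.
- Section 6.3 applies the two-weekly schedule to the whole study period, and Sections 6.4 and 6.5 repeat it for the months after withdrawal.

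Sections 4.3 and 6.3 also say what an abnormal result leads to: "this will be confirmed on a repeat blood test within 1-2 weeks and if persistent, liver biopsy will be performed".

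**The concern.** These blood tests are the main scheduled trigger for a for-cause biopsy while patients take no immunosuppression. Section 1.4 hypothesises that half of the patients will reject during minimisation or withdrawal. It also cautions that the reversibility seen in earlier, mainly calcineurin-inhibitor, withdrawal studies may not carry over to sirolimus. Section 3.4 lists the timing, severity and reversibility of rejection among the safety endpoints. The interval between tests directly affects observed timing, so if some patients were tested two-weekly and others monthly, their times to rejection would not be comparable.

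The funding text makes the slip more likely in practice. Blood and Tissue Samples in 3.1 ties study payment to interim tests that stop at withdrawal. The corresponding text in 4.3 calls the two-weekly tests standard of care, and the consent text in 3.1 charges standard-of-care tests to the patient or insurer. The screening text in 3.1 says the study pays for the interim tests. Someone budgeting or ordering tests for the off-drug year could reasonably follow the narrower sentence.

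**Working it through.** The protocol states no test count, so there is no figure of its own to reproduce.

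**Can the sentences be reconciled?** Only if complete withdrawal meant the end of the study. The screening text in 3.1 defines it as stopping the once-weekly dose, which starts the 12-month off-drug period. Blood and Tissue Samples itself separates the sample taken before complete withdrawal from the one taken a year after it. The 3.1 Follow-up sentence also conflicts with itself: the trial lasts 18 months, and withdrawal comes at about month 6.

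**Inputs**

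- Off-drug period: 12 months, or 52 weeks (3.1, 4.3, 6.4).
- Two-weekly tests in that period (3.1 screening text, 4.3, 6.4, 6.5).
- Monthly standard-of-care panel for all patients (3.1 Blood and Tissue Samples).
- Confirmation of an abnormal result within 1 to 2 weeks (4.3, 6.3).
- Assumption: the monthly metabolic panel continues after withdrawal and includes the liver tests.

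**Scheduled liver tests in the off-drug year, for a patient who stays off drug throughout**

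| Reading | Count |
|---|---|
| Every two weeks | 52 / 2 = 26 |
| Monthly panel plus one interim test per month | 12 × 2 = 24 |
| Interim tests stop, monthly panel continues | 12 |
| All scheduled laboratory follow-up stops except the month-12 and month-18 visits (6.5, 6.6) | 2 |

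The loss on the milder reading is 26 − 12 = 14 tests, and 14/26 = 54%. Counted from 24 it is 12 tests, and 12/24 = 50%. If all 25 patients completed the off-drug year, the totals would be 25 × 26 = 650 against 25 × 12 = 300.

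**Time from crossing the biopsy threshold to a confirmed abnormality**

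The worst case is the test interval plus confirmation. The mean is half the interval plus confirmation, if onset falls uniformly between tests.

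| Interval | Worst case (weeks) | Mean (weeks) |
|---|---|---|
| 2 weeks | 2 + (1 to 2) = 3 to 4 | 1 + (1 to 2) = 2 to 3 |
| 4 weeks | 4 + (1 to 2) = 5 to 6 | 2 + (1 to 2) = 3 to 4 |
| Calendar month, 4.3 weeks | 4.3 + (1 to 2) = 5.3 to 6.3 | 2.15 + (1 to 2), about 3.2 to 4.2 |

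The confirmation step is common to both schedules and cancels in the difference. The added delay is about 2 weeks at worst and about 1 week on average.

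**The case against.** The strongest reply is that the protocol settles the matter elsewhere. Two-weekly testing appears in the overview and screening text of 3.1, in 4.3 and in 6.3 to 6.5. Section 6 sets out the study procedures, so staff would probably work from it. The 3.1 Follow-up sentence itself refers back to earlier text, which includes the off-drug schedule. Section 5.1 tracks compliance against a schedule of events, and the study figure is not shown in the text available for this review, so the schedule actually used cannot be confirmed. This stands as an argument about likelihood: the delay is conditional on someone following the wrong sentences. It does not remove the contradiction, because both sentences are current operative text.

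The reply can also say that the consequence is small. The mean delay is about a week, and monthly testing is the stated standard of care. Section 1.4 adds that none of the centre's patients previously converted to sirolimus rejected or lost a graft, and that graft failure in earlier withdrawal studies was below 1%. That is fair context. However, the centre's reassuring experience concerns patients converted to sirolimus, and the standard-of-care interval was not set for patients taking no immunosuppression under this protocol.

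Finally, 12 is not the only literal result. The 3.1 Follow-up sentence alone could be read as ending all scheduled laboratory follow-up, which would leave 2 tests. That is correct, and it makes 12 the milder figure.

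**Conclusion.** The inconsistency is real and should be fixed. The two sentences in 3.1 are the ones in error, since every other statement of the schedule continues two-weekly testing. Following them would at least halve scheduled liver testing off drug, from 24 to 26 tests down to about 12. These counts apply only to patients who stay off sirolimus for the whole year, and the 12 rests on the assumption about the monthly panel given above.

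The effect is on when rejection is detected. The conflict does not by itself leave failures uncounted in the primary endpoint, because Sections 4.3 and 6.6 give patients presumed tolerant a biopsy at 12 months off drug. Sample size and error rates are unaffected.

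**What to change.** Delete the last three words of both sentences in Section 3.1 (the Follow-up sentence and the interim-test sentence in Blood and Tissue Samples), so that two-weekly liver tests run through the 12 months off drug, as 4.3, 6.4 and 6.5 already require.

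In the same place, state that study funds cover the interim tests for the whole study. This repeats what the 3.1 screening text says, but it removes the doubt created by the standard-of-care label in 4.3.

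As minor tidying, use one description of the panel in 3.1 and 4.3. The two-weekly panel is variously given as liver tests only, blood count plus liver tests, and blood count plus metabolic panel. A workable wording is a monthly blood count and metabolic panel, with liver tests only at the interim draws.

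The cost is one phrase deleted in two sentences, one funding sentence and the optional tidying. No test is added beyond those already required.

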The primary outcome will be the proportion of patients off SRL therapy with normal liver biochemistry and graft histology at 12 months (i.e. tolerant). Thus, the incidence of graft dysfunction (acute rejection, immune mediated or autoimmune hepatitis, chronic rejection) or non-tolerance will be assessed in this SRL withdrawal group and compared to the historical CNI group (20% tolerant; 80% failure) as the primary endpoint. This rate will be a composite of the cumulative number of biopsy-proven graft dysfunctions requiring conversion back to SRL or additional IS therapy or discontinuation of minimization/withdrawal that occur during the course of the study. Major secondary measures compared will be the predictive capacity of the blood and graft biomarker assays (immunophenotyping, genomic/proteomics) before and after minimization/withdrawal in the success vs. failure groups. Clinical secondary outcomes will be compared: the number of infectious complications, liver biopsy complications, cardiovascular outcomes (i.e. blood pressure, diabetes control, lipid levels), renal function, hematopoietic parameters, gastrointestinal effects, or other side effects of SRL that may or may not improve or develop with minimization/withdrawal. These will all be documented by a study database during patient visits, electronic charts and/or by phone communication. Finally, quality of life (Post Liver Transplant Quality of Life Instrument (pLTQ) and the Promis-29 profile v1.0) will be analyzed at the end of the study to determine the effect of IS minimization/withdrawal on other health benefits.

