3.2 Primary Study Endpoints

The primary outcome will be the proportion of tolerant patients off SRL therapy with normal liver biochemistry and graft histology at 12 months.

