Laboratory follow-up (CBC, CMP) is described above- every 2 weeks throughout the trial. Any biochemical (or clinical) signs or significant liver function test abnormalities will be acted on immediately either by liver biopsy or resumption of the recent IS dose. All patients will be seen in the clinic every 3 months to assess for any new signs or symptoms or resolution of drug side effects in the minimization or withdrawal arm. The Post Liver Transplantation Quality of Life and Promis-29 quality of life surveys and IS cost tally will be performed prior to the study onset and after successful vs. unsuccessful withdrawal (end of study).

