7.2 Statistical Methods

We have performed within subject comparisons and measurements on PBMC and biopsy using appropriate paired analysis (paired t-test or equivalent nonparametric test (Wilcoxon Signed Rank test) (12, 13). Repeated measures of analysis of variance (RM-ANOVA) were used to test the trajectory variations over time. Two-sided F-test statistics were applied using $\alpha=0.05$. For proteogenomic bioinformatics analysis, we have reported for each gene/protein comparison the T-test p-value, its non-parametric analog (Kruskal Wallis test), the fold change, and for multi-analyte signatures, the AUROC curve (C-index) and the q-values by member genes/proteins. We were then able to calculate the predictive accuracy, sensitivity and specificity of each signature. For clinical endpoints, categorical and continuous variables will be analyzed with appropriate tests (Fisher's exact, T-test). $P<0.05$ will be considered significant

7.3 *Subject Population(s) for Analysis*

All subjects (successful vs. failed, withdrawn from the study vs. maintained) will be followed and analyzed at study end. We will also document the number of patients screened who did not meet I/E criteria at the study initiation.

8 Safety and Adverse Events

8.1 *Definitions*

Adverse Event

By definition an **adverse event** (AE) is defined as: any symptom, sign, illness or experience that develops or worsens in severity during the course of the study. Intercurrent illnesses or injuries should be regarded as adverse events. Abnormal results of diagnostic procedures are considered to be adverse events if the abnormality:

- results in study withdrawal
- is associated with a serious adverse event
- is associated with clinical signs or symptoms
- leads to additional treatment or to further diagnostic tests
- is considered by the investigator to be of clinical significance

Adverse events are classified as serious or non-serious.

Serious Adverse Event

. A **serious adverse event** is any AE that is:

- fatal
- life-threatening
- requires or prolongs hospital stay
- results in persistent or significant disability or incapacity
- a congenital anomaly or birth defect
- an important medical event

Events that are expected, anticipated, related to the standard of care treatment or known adverse events/serious adverse events from standard of care medications or pre-existing conditions will not be reported.

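### Section 3.1 (Outcome Measures) defines the rate compared with 20%/80% as a count of biopsy-proven dysfunctions, which is not the complement of the tolerant proportion in 3.2

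*Combined protocol and SAP*

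**What the plan says.** Outcome Measures in 3.1 opens with a definition that requires proof of success: "The primary outcome will be the proportion of patients off SRL therapy with normal liver biochemistry and graft histology at 12 months (i.e. tolerant". Section 3.2 repeats it: "proportion of tolerant patients off SRL therapy with normal liver biochemistry and graft histology at 12 months". The Study Summary agrees. The General Design text says 18 months, but that is only a difference of label, because 6.6 places the 18-month visit 12 months after withdrawal.

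The next sentence of Outcome Measures, presented as a consequence, says that graft dysfunction or non-tolerance will be "compared to the historical CNI group (20% tolerant; 80% failure) as the primary endpoint". The sentence after that says what the rate is made of: "a composite of the cumulative number of biopsy-proven graft dysfunctions requiring conversion back to SRL or additional IS therapy or discontinuation of minimization/withdrawal".

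Other sections bear on who can fall between the two definitions:

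- 4.3 (Follow-up) says abnormal liver tests will be "acted on immediately either by liver biopsy or resumption of the recent IS dose". 4.3 (Screening Evaluation) says of liver dysfunction that "this will be confirmed on a repeat blood test within 1-2 weeks and if persistent, liver biopsy will be performed".
- 4.3 and 6.6 say that "patients developing rejection or resumption of IS prior to this period will not have a final liver biopsy performed".
- 4.4.1 lets patients leave by choice or be removed for non-compliance. 4.4.2 lists survival, laboratory values and immunosuppression for them, but not histology.
- 7.3 says "All subjects (successful vs. failed, withdrawn from the study vs. maintained) will be followed and analyzed at study end". It gives no rule for classing a patient without 12-month histology. 7.2 names no specific analysis of the primary proportion against 20%.

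**The concern.** One definition needs proof of success (off sirolimus, normal biochemistry, normal histology). The other needs proof of failure (a biopsy-proven dysfunction with a treatment consequence). A patient with neither proof is not shown tolerant under 3.2 and is not a failure under the composite. The composite is also a cumulative number of dysfunctions, so one patient could contribute more than once, and a count is not a proportion.

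The 20% figure is the trial's only external benchmark for success. General Design says that a rate below about 20% would argue against larger trials, and that the results are to guide a submission for them. If an analyst follows the composite sentence and takes its complement as tolerance, unproven patients enter the result as successes. If the choice between the two definitions is made after the data are seen, it could decide on which side of 20% the result falls.

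**Working it through.** **1. Who falls in the gap.**

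| Patient | 3.2: shown tolerant? | Composite failure? |
|---|---|---|
| Off immunosuppression, final biopsy missing or declined (each biopsy needs separate consent) | No | No |
| Leaves the study, no 12-month histology | No | No, unless a dysfunction was proven or, on the separate-limb reading, withdrawal was discontinued |
| Abnormal biochemistry or histology at 12 months, no change in immunosuppression | No | No |
| Resumes immunosuppression without a biopsy | No, unless later withdrawn again | Depends on parsing |

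The third group is narrow, because 4.3 and 6.6 restart immunosuppression for rejection or immune-mediated hepatitis. The fourth is limited, because 3.1, 4.3 and 6.3 provide for-cause biopsies. It is in the gap only if discontinuation of minimization or withdrawal must itself be biopsy-proven. If discontinuation is a separate limb, these patients are failures, but the other groups remain. So the composite is not the complement under either parsing.

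**2. Direction.** Suppose the composite is biopsy-proven and counted once per patient. 3.1 and 4.3 allow no second withdrawal attempt after rejection, and 4.3 extends this to immune-mediated hepatitis. A composite failure then does not meet 3.2, so 1 minus the composite is equal to or greater than the 3.2 proportion. If discontinuation is a separate limb, a patient who resumed immunosuppression without a biopsy is a failure, yet no section bars a later re-taper. Overstatement is then likely but not guaranteed. Counting repeat events per patient would push the other way.

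**3. Size per patient.** The documents give no figure to reproduce: 7.1 states no power, formula or cut-off. Inputs are n = 25 (Study Summary; up to 25 in 3.1), 20% (3.1) and the >20% objective (Study Summary). Each gap patient adds 1/25 = 4 points, and more if fewer enrol.

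- Against >20%: 5/25 = 20% becomes 6/25 = 24% with one gap patient.
- Against the <20% wording in General Design: 4/25 = 16% becomes 5/25 = 20%.
- Illustration with 8 shown tolerant, 4 unproven and 13 composite failures: 8/25 = 32% (exact 95% CI 15-54%) becomes 12/25 = 48% (28-69%). If all 4 are missing final assessments, excluding them gives 8/21 = 38% (18-62%).

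**4. How often the answer to >20% changes.** Let p be the true 3.2 proportion and g the proportion of patients in the gap (assumed 4%, 8% or 16%). With the gap counted as success, X ~ Binomial(25, p + g), and an observed rate above 20% means X ≥ 6.

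At p = 20%, P(X ≥ 6) is 38.3% with no gap, and 57.7%, 74.1% or 93.2% with the three gaps.

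The probability that the answer changes is P(X ≤ 5 | p) − P(X ≤ 5 | p + g):

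| p | g = 4% | g = 8% | g = 16% |
|---|---|---|---|
| 30% | 9.4% | 14.8% | 18.7% |
| 40% | 1.8% | 2.6% | 2.9% |
| 50% | 0.15% | 0.19% | 0.20% |

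The 50% row corresponds to 1.4, which hypothesises that half of patients will reject.

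**The case against.** The strongest reply is that the plan means one thing. The Study Summary, General Design, the first sentence of Outcome Measures and 3.2 all name the tolerant proportion. The linking sentence names non-tolerance and is framed as following from that definition, which suggests that failure is simply its complement. Nothing says that 1 minus the composite will be reported as tolerance. This stands as evidence of intent, but the next sentence gives the rate a narrower content, so the text still contradicts itself.

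Three stronger readings are tempting, and the documents do not support them:

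- That only the composite is tied to 20%. The Study Summary, 1.1, 1.3 and General Design also set the success or tolerance rate against 20%.
- That the composite can only overstate tolerance. The ban on a second attempt covers rejection and immune-mediated hepatitis, not immunosuppression resumed without a biopsy.
- That 3.2 and 7.3 already class every unproven patient as non-tolerant. 3.2 states no denominator and 7.3 no classification rule, so missing histology is a problem under either definition.

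Two further objections stand as limits. First, 1.4 describes the historical 80% as rejection requiring immunosuppression to be reinstated, which resembles the composite more than 3.2. The documents do not give the source's definition of failure. Second, normal is undefined. The entry criteria in 4.2 admit enzymes below twice the upper limit and histology below grade 2 or stage 2, so a patient unchanged since entry might be scored non-tolerant.

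**Conclusion.** The point holds as an internal contradiction in the primary endpoint that should be fixed. The rate described for the historical comparison is not the complement of the 3.2 proportion under either parsing, and it counts events. Read as biopsy-proven and per patient, it tends to overstate tolerance; on the separate-limb reading that direction is likely rather than certain.

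The size is 4 points per gap patient at n = 25. The number of such patients is not in the documents, so the gaps of 4-16% are assumptions. An observed rate above 20% is used here as a yardstick taken from the objective; section 7 states no decision rule. The answer is sensitive when true tolerance is near 20-30%. At the hypothesised 50% it changes with probability of at most 0.2%, although the estimate would still be too high by the size of the gap.

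**What to change.** - **3.1, Outcome Measures:** replace the composite sentence. The rate compared with 20% is the 3.2 proportion, counted per patient over all patients who start minimization, with failure as its exact complement. Use the same label, 12 months after withdrawal, in General Design.
- **7.3:** state that a patient without documented normal biochemistry and histology, off immunosuppression, 12 months after withdrawal counts as non-tolerant. This includes immunosuppression resumed without a biopsy, study withdrawal and a missing final biopsy.
- **7.2:** report the proportion with an exact 95% CI, and add a sensitivity analysis that excludes patients with a missing final assessment.
- **Secondary rate:** report biopsy-proven graft dysfunction requiring immunosuppression, once per patient, alongside the 80% as 1.4 describes it.

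The passages on the response to abnormal liver tests (biopsy or pause in 3.1, biopsy or resumption in 4.3, repeat test then biopsy in 4.3 and 6.3) should also be reconciled, because they determine who has a biopsy. Which response is right is a clinical matter outside this point.

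The cost is wording and analysis, with no added procedures. There are two downsides. Counting unknowns as failures may understate tolerance by up to 4 points each, and the sensitivity analysis shows how much the missing assessments matter. The 3.2 rate may also be stricter than the historical definition of failure, so the report should say that the match to the benchmark is uncertain. The meaning of normal still has to be settled by the sponsor.
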